13.4 Methods of Analysis

Baseline characteristics of the subjects will be described using summary statistics overall and by treatment group (Part 2 only).

All continuous variables will be reported with number of subjects, mean, median, SD, minimum and maximum. All categorical variables will be summarized with number of subjects and frequency.

For Part 1, all endpoints will be summarized with descriptive statistics. Based on the characteristics of the study design and lack of a concurrent control arm, formal testing of treatment effects will not be performed. However, some measures will be summarized by both point estimates and the estimation of 95% confidence limits, where appropriate.

All statistical tests for Part 2 will be conducted at a 1-sided significance level of 2.5% unless otherwise specified.

The primary analysis of Part 2 will occur after all subjects have completed Day 56 of Part 2 or discontinued from study treatment, the Adjudication Committee has adjudicated all data through Day 56 of Part 2 and the study has been unblinded. The primary analysis will evaluate the primary outcome measure and all other outcome measures up to the data cutoff. A final analysis of the secondary and exploratory outcome measures will occur after all subjects have completed or discontinued from the study.

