13. STATISTICS

13.1 Sample Size and Power Calculations

Part 1:

The sample size for Part 1 was determined from an operational perspective and was not based on statistical power considerations. With 20 evaluable subjects and an assumed true response rate of 65%, the probability of observing an overall response rate of at least 55% is 87.8%. If the true response rate is 40%, the probability of observing an overall response rate of 55% or higher is less than 13%.

Part 2:

The primary endpoint for Part 2 is the overall response rate at Day 28.

The null hypothesis for Part 2 is that there is no difference in the overall response rate at Day 28 between the 2 treatment groups. The alternative hypothesis is that the overall response rate at Day 28 of the GLASSIA group is higher than that of the control group.

To determine the sample size for Part 2, the following assumptions were used:

1. Control group overall response rate of 40% across strata
2. GLASSIA group overall response rate of 65% across strata
3. Randomization ratio 1:1
4. 1-sided family wise Type I error rate of 0.025
5. Type II error rate of 0.20 (ie, power=80%)
6. A group sequential design with 1 interim look will be applied to the study. The gamma error spending function³¹ with a parameter -2 will be used for beta spending (nonbinding). The interim analysis will take place when approximately 50% of the primary endpoint data has been accumulated

SAS version 9.4, PROC SEQDESIGN with stop=both and nonbinding option for beta, and a gamma parameter of -40 for alpha spending (and hence no alpha spent) and -2 for beta spending was used to calculate this design.

Based on the sample size calculations, using a Cochran-Mantel-Haenszel chi-squared test, controlling the stratification factor, to detect the difference between the 2 groups, the primary analysis will require 67 evaluable subjects per group. Assuming a 10% early withdrawal rate, the target number of subjects will include 74 randomized subjects per group for a total of 148 randomized subjects.

The early withdrawal rate will be monitored in a blinded manner, and if found to be greater or less than 10%, sample size assumptions may be revised.

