13.4.2 Secondary Outcome Measures

Part 1

The secondary efficacy outcome measures (see Section 8.4.2.1) and the secondary PK outcome measures (see Section 8.4.2.3) will be summarized with descriptive statistics. PK parameters will be summarized with the mean, SD, median, minimum and maximum values, geometric mean and percentage of coefficient of variation.

Part 2

The key secondary endpoint of GI response rate at Day 28 (see Section 8.4.2.1) and all binary types of endpoints, including overall response at Day 56, will be analyzed similarly to the overall response rate at Day 28.

Other secondary endpoints that will be derived in the statistical analyses include, but are not limited to, the following:

- All-cause, transplant-related, infection-related and GvHD-related mortality: defined as the time from HSCT to death due to any cause, transplantation, infection and GvHD, respectively
- Duration of any overall and GI response

The secondary endpoints of overall survival and failure-free survival rate at different timepoints will be analyzed using the Cox proportional hazard model. The hazard ratio (and the corresponding 95% confidence interval) will be reported. A Kaplan-Meier plot will also be presented. All-cause, transplant-related, infection-related and GvHD-related mortality will be analyzed using a similar method with competing-risk taken into consideration.

The other time-to-event types of secondary endpoints, including duration of any overall response and any GI response, will also be analyzed using the Cox proportional hazard model and summarized using Kaplan-Meier plots.

The change from baseline in acute GvHD grading will be analyzed with a shift table.

All other secondary efficacy endpoints will be summarized with descriptive statistics.

Safety Analyses (Parts 1 and 2)

Secondary safety outcome measures will be summarized with descriptive statistics and qualitative analysis (see Section 8.4.2.2). Adverse events will be listed for each subject and summarized by system organ class and preferred term by using the Medical Dictionary for Regulatory Activities. Safety laboratory data, vital signs measurements and biomarker data will be listed for each subject and summarized with descriptive statistics by treatment group (Part 2 only), visit and assessment time.

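### The family behind the one-sided 0.025 is not defined and the key secondary has no testing order, so the error rate is controlled for the primary endpoint only

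*Protocol*

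**What the plan says.** Section 13.1 of the protocol lists the Part 2 sample-size assumptions. Among them is a "1-sided family wise Type I error rate of 0.025", next to a group sequential design with one interim look. That section names one endpoint, Day 28 overall response, and one null hypothesis.

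Section 13.4 sets the level for testing: "All statistical tests for Part 2 will be conducted at a 1-sided significance level of 2.5% unless otherwise specified". The synopsis repeats the rule.

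Section 13.4.2 starts its Part 2 text with "The key secondary endpoint of GI response rate at Day 28". It gives that endpoint, and binary endpoints such as Day 56 overall response, the same kind of analysis as the primary. Cox models are assigned to overall survival, failure-free survival and the two response durations, and a similar method allowing for competing risks to the four mortality endpoints. Acute GvHD grading gets a shift table. The remaining secondary efficacy endpoints, the safety measures and (section 13.4.3) the exploratory measures are descriptive.

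No hierarchy, gate or split of alpha appears in either document. SAP section 1 says that the SAP covers Part 1 only and that there will be none for Part 2. SAP section 5 plans no formal testing for Part 1.

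**The concern.** A family-wise error rate means something only once the family is named. The plan names the rate and leaves the family open, then gives the full 2.5% to the key secondary and to each other tested secondary endpoint, with no condition linking them to the primary.

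The key secondary is the test that matters most. The protocol ranks GI response above the other secondary endpoints (8.4.2.1), gives it its own rationale (8.4.4) and applies the treatment-failure rule to it alongside the primary (8.2). The Part 2 secondary objective in 7.3.1 is worded as determining efficacy against control. Under the rule as written, a GI response result with one-sided p below 0.025 after a failed primary could be presented as significant at the plan's stated level, and no sentence rules that out.

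**Working it through.** **Step 1. Reproduce the plan's own design.** Inputs from section 13.1: "Control group overall response rate of 40% across strata"; "GLASSIA group overall response rate of 65% across strata"; "Randomization ratio 1:1"; one-sided alpha 0.025; type II error 0.20; one look at information fraction 0.5; gamma parameters -40 (alpha) and -2 (beta, nonbinding).

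- Beta spent at the interim: 0.20 × (1 − e^1)/(1 − e^2) = 0.0538. Section 13.5 states 0.0538.
- Final critical value 1.960. The drift that gives a total type II error of 0.20 over the two looks, solved numerically, is 2.8475.
- Futility boundary: 2.8475 × √0.5 + z(0.0538) = 0.404, a nominal one-sided p of 0.3430. Section 13.5 states 0.3430.
- Log odds ratio: ln[(0.65/0.35)/(0.40/0.60)] = 1.0245. Variance term: 1/(0.40 × 0.60) + 1/(0.65 × 0.35) = 8.562.
- N per group: 2.8475² × 8.562/1.0245² = 66.1, rounded up to 67. Section 13.1 states 67.

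All three stated figures are reproduced.

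**Step 2. Type I error for the primary alone.** Alpha spent at the interim: 0.025 × (1 − e^20)/(1 − e^40), about 5 × 10⁻¹¹. The final test therefore keeps the whole 0.025. If the futility rule is always obeyed, the error falls slightly, to 0.0239. For Day 28 overall response the 0.025 holds across both looks.

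**Step 3. Add the key secondary.** Each test is at one-sided 0.025, neither conditions on the other, and both nulls are true. The probability of at least one rejection is 1 − P(Z1 < 1.96 and Z2 < 1.96), with Z1 and Z2 bivariate normal with correlation ρ. At ρ = 0 this is 1 − 0.975² = 0.0494.

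| Assumed ρ | Error for the pair |
|---|---|
| 0 | 0.0494 |
| 0.5 | 0.0454 |
| 0.7 | 0.0417 |
| 0.9 | 0.0352 |

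The range is 0.0352/0.025 = 1.4 to 0.0494/0.025 = 2.0 times the stated rate. Adding Day 56 overall response as a third test at equal pairwise correlations gives 0.073, 0.063, 0.055 and 0.042 at the same four values (simulated, except the first).

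**Step 4. Check the remedy.** In a fixed sequence of primary then GI response, suppose first that the primary null is true. Any false rejection in the pair then requires rejecting the primary, which has probability at most 0.025. If only the GI null is true, the false rejection is the GI test itself, again at most 0.025. The pair is controlled at 0.025 for any correlation. The primary keeps its critical value of 1.960 and its 67 per group. A Bonferroni split at 0.0125 each, put through the same calculation as Step 1, would need about 80 evaluable per group (79.9 rounded up).

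**The case against.** The strongest reply is that nothing stated is false. The family-wise phrase occurs only in the Part 2 sample-size assumptions (13.1 and the matching synopsis paragraph), which concern a single endpoint in a group sequential design. The design was computed with stopping boundaries for both errors and an explicit alpha-spending function, so overall error across two looks is an ordinary meaning of the phrase, and Step 2 shows that it holds. This stands. A reader might infer that, because the interim spends no alpha, the phrase can only refer to endpoints and the claim is therefore broken. The documents do not support that inference.

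A reader might also take section 13.4 to mean that every Part 2 endpoint is tested at 2.5%. It does not say so. It sets a default level for the tests that are done, and 13.4.2 and 13.4.3 leave many measures descriptive.

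The size can be overstated as well. The 4.9% figure needs independence, which is unlikely here. Every subject must have lower GI involvement (9.1), both responses are judged in the same subjects on the same day, and a treatment failure counts as a non-response on both (8.2). The upper part of the correlation range is therefore plausible, though the two response definitions differ and the correlation is below 1.

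Finally, the protocol nowhere says that a secondary endpoint may support a claim after a failed primary, and Part 2 never began. Both are true, and they limit the weight of the point. They do not supply the missing rule: key secondary is a rank, not a testing procedure.

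**Conclusion.** The point holds in limited form. The plan leaves the family undefined and gives the key secondary no place in a testing order, so one-sided 0.025 is controlled for the primary endpoint only. If the family includes GI response at Day 28, the error is about 3.5% to 4.9% when both nulls are true, for assumed correlations from 0.9 down to 0. Every value in that range exceeds 2.5%, but calling it roughly double is fair only near independence.

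This is not a finding that the primary analysis or its sample size is wrong: both were reproduced and the primary's error rate is sound. The practical weight is low, because SAP section 1 records that the study was terminated before Part 2 started. The point matters for the protocol as a record and for any reuse of the design.

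**What to change.** In section 13.1, define the family as Day 28 overall response and Day 28 GI response. In section 13.4, and in the synopsis, add: GI response at Day 28 is tested at one-sided 2.5% only if the Day 28 overall response test is significant (fixed sequence); for all other tested secondary endpoints (Day 56 response, the time-to-event endpoints and the mortality endpoints) p-values are nominal and carry no confirmatory claim.

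The cost is that a GI response result cannot be claimed as confirmatory if the primary fails. Primary power, the 67 evaluable subjects per group and the interim rule are unchanged.

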13.4.1 Primary Outcome Measure

Part 1

The overall response rate at Day 28 (see Section 8.4) will be summarized with descriptive statistics for Part 1 of the study. The primary analysis will use the Efficacy Analysis set, with sensitivity analyses carried out on the Per Protocol Analysis set and SAF set. A subgroup analysis of baseline lower GI involvement severity (stage 1 to 2 or stage 3 with no other organ involvement, stage 4 or stage 3 with other organ(s) involved) will be performed.

Part 2

The overall response rate at Day 28 (see Section 8.4) will be analyzed using the Cochran-Mantel-Haenszel chi-squared test, controlling the stratification factor (lower GI involvement severity), to test the null hypothesis that the odds ratio is equal to 1 for Part 2 of the study. To maintain the power of the study, the gamma error spending function³¹ with a parameter -2 will be used for type II error.

An unstratified comparison of the overall response rate at Day 28 will be conducted as a sensitivity analysis.

13.4.2 Secondary Outcome Measures

Part 1

The secondary efficacy outcome measures (see Section 8.4.2.1) and the secondary PK outcome measures (see Section 8.4.2.3) will be summarized with descriptive statistics. PK parameters will be summarized with the mean, SD, median, minimum and maximum values, geometric mean and percentage of coefficient of variation.

Part 2

The key secondary endpoint of GI response rate at Day 28 (see Section 8.4.2.1) and all binary types of endpoints, including overall response at Day 56, will be analyzed similarly to the overall response rate at Day 28.

Other secondary endpoints that will be derived in the statistical analyses include, but are not limited to, the following:

- All-cause, transplant-related, infection-related and GvHD-related mortality: defined as the time from HSCT to death due to any cause, transplantation, infection and GvHD, respectively
- Duration of any overall and GI response

The secondary endpoints of overall survival and failure-free survival rate at different timepoints will be analyzed using the Cox proportional hazard model. The hazard ratio (and the corresponding 95% confidence interval) will be reported. A Kaplan-Meier plot will also be presented. All-cause, transplant-related, infection-related and GvHD-related mortality will be analyzed using a similar method with competing-risk taken into consideration.

The other time-to-event types of secondary endpoints, including duration of any overall response and any GI response, will also be analyzed using the Cox proportional hazard model and summarized using Kaplan-Meier plots.

The change from baseline in acute GvHD grading will be analyzed with a shift table.

All other secondary efficacy endpoints will be summarized with descriptive statistics.

Safety Analyses (Parts 1 and 2)

Secondary safety outcome measures will be summarized with descriptive statistics and qualitative analysis (see Section 8.4.2.2). Adverse events will be listed for each subject and summarized by system organ class and preferred term by using the Medical Dictionary for Regulatory Activities. Safety laboratory data, vital signs measurements and biomarker data will be listed for each subject and summarized with descriptive statistics by treatment group (Part 2 only), visit and assessment time.

For the purpose of summaries and listings, the durations of AEs will be calculated as follows: $(stop\ day - start\ day) + 1\ day$, which yields the number of days on which the AE was present.

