The sample size for Part 2 is based on the assumptions of a control group overall response rate of 40% across strata; GLASSIA group overall response rate of 65% across strata; randomization ratio 1:1; 1-sided family wise Type I error rate of 0.025; Type II error rate of 0.20; and a group sequential design with 1 interim look. Based on the sample size calculations, using a Cochran-Mantel-Haenszel chi-squared test, controlling the stratification factor, to detect the difference between the 2 groups, the primary analysis will require 67 evaluable subjects per group. Assuming a 10% early withdrawal rate, the target number of subjects will include 74 randomized subjects per group for a total of 148 randomized subjects.

Planned Statistical Analysis

For Part 1, all endpoints will be summarized with descriptive statistics.

For Part 2, all statistical tests will be conducted at a 1-sided significance level of 2.5% unless otherwise specified. For Part 2, the primary endpoint of overall response rate at Day 28 will be analyzed using the Cochran-Mantel-Haenszel chi-squared test, controlling the stratification factor (lower GI involvement severity), to test the null hypothesis that the odds ratio is equal to 1 for Part 2 of the study. An unstratified comparison of the overall response rate at Day 28 will be conducted as a sensitivity analysis. The binary types of secondary efficacy endpoints, such as GI response rate, will be analyzed similarly to the primary endpoint. The time-to-event type of secondary endpoints, including overall survival and failure-free survival rate; all-cause, transplant-related, infection-related and GvHD-related mortality; and durations of any overall and any GI response will be analyzed using the Cox proportional hazard model. The change from baseline in acute GvHD grading will be analyzed with a shift table. All other secondary endpoints will be summarized with descriptive statistics.

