8.4.2 Secondary Outcome Measures

8.4.2.1 Efficacy (Parts 1 and 2)

Key Secondary Efficacy Outcome Measures

1. Proportion of subjects achieving GI response at Day 28. Gastrointestinal response is defined as GI CR + PR, which are defined as follows:
 - GI CR is defined as
 - a) Able to eat; not requiring parenteral nutrition, and
 - b) Passing primarily formed stools
 - GI PR is defined as
 - a) Decrease in need for parenteral nutrition to $\leq 50\%$ of required calories; and
 - b) Reduction of stool volume by $\geq 50\%$, without ileus

Other Secondary Efficacy Outcome Measures

1. Proportion of subjects achieving overall response at Day 56
2. Change from baseline in acute GvHD grading at Days 28, 56 and 180
3. Incidence of chronic GvHD at Days 100, 180 and 365

4. Duration of any overall response
5. Duration of any GI response
6. Overall survival through Days 100, 180 and 365
7. Transplant-related mortality at Days 28, 56, 100 and 180
8. Failure-free survival at Days 100 and 180
9. GvHD-free survival at Days 28, 56, 100 and 180
10. Infection-related mortality at Days 28, 56, 100 and 180
11. GvHD-related mortality at Days 28, 56, 100 and 180
12. All-cause mortality at Days 28, 56, 100 and 180

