8.5 Randomization and Blinding

8.5.1 Randomization

Part 1 is a nonrandomized, open-label, active treatment clinical study. In Part 1, if the subject has met all eligibility criteria, the Eligibility Criteria Form will be completed by the site, signed by the investigator and faxed to the Medical Monitor for review. The form must be signed by the Medical Monitor prior to proceeding with enrolling the subject in the Interactive Response Technology (IRT).

Part 2 is a randomized, double-blind, concurrent, placebo (albumin)-controlled clinical study. In order to minimize/avoid bias, subjects will be randomly assigned to 1 of 2 treatment regimens (investigational product [IP] or control) in equal numbers. Randomization codes will be maintained by the sponsor or the sponsor's representative.

In Part 2, if the subject has met all eligibility criteria, the Eligibility Criteria Form will be completed by the site, signed by the investigator and faxed to the Medical Monitor for review. The form must be signed by the Medical Monitor prior to proceeding with randomizing the subject. The site will then request the study treatment assignment using the IRT system.

All randomized subjects will be managed by IRT. The IRT will assign subjects their 6-digit subject number at the time of randomization and will provide the vial number of the blinded study treatments to be administered at each visit. Subjects will not be re-randomized.

Subjects will be randomized to treatment via stratified randomization, using a single stratification factor. Separate randomization schedules will be used within each strata of lower GI involvement severity, based on the modified IBMTR grading system (Section 11.4). The 2 strata will be as follows:

- Lower GI Stage 4, or Stage 3 with other organ(s) involved
- Lower GI Stage 1 to 2, or Stage 3 with no other organ involvement

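### The Part 2 Cox and competing-risk analyses do not name the randomisation stratum, and duration of response gets a two-arm Cox model without a Part 2 definition

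*Protocol*

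**What the plan says.** **Randomisation.** Protocol 8.5.1: "Separate randomization schedules will be used within each strata of lower GI involvement severity". There are two strata: Stage 4, or Stage 3 with other organs involved, against Stage 1 to 2, or Stage 3 alone.

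**Primary and binary endpoints.** Protocol 13.4.1 tests Day 28 response with a Cochran-Mantel-Haenszel test that controls the stratum, and adds an unstratified comparison as a sensitivity analysis. Protocol 13.4.2 extends the same approach to GI response and the other binary endpoints, and to those only.

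**Time-to-event endpoints.** Protocol 13.4.2: "The secondary endpoints of overall survival and failure-free survival rate at different timepoints will be analyzed using the Cox proportional hazard model". Mortality "will be analyzed using a similar method with competing-risk taken into consideration"; the type of competing-risk model is not given. The other time-to-event endpoints, "including duration of any overall response and any GI response, will also be analyzed using the Cox proportional hazard model". The synopsis agrees: "durations of any overall and any GI response will be analyzed using the Cox proportional hazard model". No stratum or covariate appears in any of these sentences.

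**Duration of response.** Protocol 8.4.2.1 lists "Duration of any overall response" and its GI counterpart by name only, and 13.4.2 repeats them as a bare bullet. The only definition is in SAP 7.2.2: from first response to progression or death, censored at the last response assessment, in responders. SAP section 1 limits that document to Part 1 and says that no Part 2 SAP will follow, because the study was terminated before Part 2 began.

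**The concern.** The stratum was chosen for randomisation because severity is expected to matter for outcome. A Cox model that leaves out a prognostic factor estimates an HR averaged over a mixture of risks. That average lies nearer 1 than the HR within strata, and the test has less power. Protocol 13.4.2 commits to reporting the HR with its 95% confidence interval, so the estimate is affected as well as the test.

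Duration of response raises a different problem. A subject who never responds has no duration, so a Cox comparison of durations needs a stated population. If the Part 1 definition were carried over, the comparison would be between groups formed after randomisation. The design itself assumes that these groups differ in size: 40% of controls against "GLASSIA group overall response rate of 65% across strata" at Day 28. The additional GLASSIA responders may be patients whose responses last a shorter or a longer time, and the HR would then depart from 1 even if the drug had no effect on how long a response lasts.

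**Working it through.** **The plan's own figures.** Protocol 13.1 sizes only the primary endpoint, and those figures reproduce.
- Interim beta spend: 0.20 × (1 − e¹)/(1 − e²) = 0.0538, with futility p = 0.3430, both as stated in 13.5.
- The group sequential drift is 2.8475. On the log-odds-ratio scale, n per group = 2.8475² × [1/(0.40 × 0.60) + 1/(0.65 × 0.35)] / [ln(0.65 × 0.60/(0.40 × 0.35))]² = 8.108 × 8.562/1.0496 = 66.1, so 67 as stated.
- No event count, HR or power is given for any time-to-event endpoint. Every input below is therefore an assumption, apart from the 148 subjects, 1:1 allocation, two strata, 1-sided 2.5% level and assessment days.

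**Stratum: set-up.** 148 subjects, blocks of 4 within strata of 76 and 72. Exponential survival with control hazard −ln(0.55)/180 = 0.0033 per day at the midpoint of the strata. The severe-to-mild HR is r, and the true treatment HR is 0.60. A Wald test at 1-sided 2.5% is applied to the Cox model with and without the stratum, with 4,000 to 6,000 simulated trials per cell. The standard error of one power figure is at most √(0.5 × 0.5/4,000) = 0.8 points.

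**Stratum: results (power without v with the stratum).** Protocol 8.4.2.1 sets Day 365 for overall survival only. Failure-free survival and mortality end at Day 180. Ranges are the spread between repeat runs.

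| r | To Day 365 | HR without stratum, Day 365 | To Day 180 | To Day 100 |
|---|---|---|---|---|
| 2 | 63 v 67% | 0.61 to 0.62 | 45 to 47 v 47 to 49% | 29 v 30% |
| 3 | 57 v 67% | 0.64 | 42 to 44 v 47 to 49% | 30 v 33% |
| 4 | 50 v 66% | 0.66 | 40 to 41 v 49 to 50% | 30 v 35% |

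- At r = 1 the two models agree (67 v 66 to 67%), so naming a stratum that turns out not to matter costs nothing visible.
- With no treatment effect, the model without the stratum rejects in 0.011 to 0.027 of trials, so type I error is not inflated.
- With 30% of subjects in the severe stratum, Day 365 power at r = 2, 3 and 4 is 60 v 64%, 52 v 60% and 46 v 59%.
- Over true HR 0.5 to 0.7 and control 180-day survival 40 to 70%, the Day 365 gain is 1.5 to 5, 5 to 12 and 8 to 20 points.
- With fewer deaths (57 to 62 in a year), power at r = 2, 3 and 4 is 47.6 v 49.5%, 44.1 v 48.8% and 40.2 v 47.9%, so the gain is 1.9, 4.7 and 7.7 points.
- At Day 180 with control survival 70%, the gain is about 0.5, 2 and 5 points.

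**Duration: illustration on the responders-only reading.** Take 74 per arm, no true effect on duration, and every control responder also a responder on GLASSIA. At 40% v 65% there are 0.40 × 74 = 29.6 and 0.65 × 74 = 48.1 responders, and 25/65 = 38% of GLASSIA responders are additional. If these lose response at m times the hazard of the others, the HR at the start is (40 + 25m)/65. This gives 0.87, 1.19, 1.38 and 1.77 at m = 0.67, 1.5, 2 and 3. The fitted Cox HR moves back towards 1 over time when m exceeds 1, because the faster losers leave first. With median duration 173 days and censoring at 150 days:

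| Response rates | m = 0.67 | m = 1.5 | m = 2 | m = 3 |
|---|---|---|---|---|
| 40% v 65% (Day 28 design rates) | 0.87 | 1.18 | 1.34 | 1.55 |
| 55% v 70% (assumed) | 0.92 | 1.10 | 1.18 | 1.29 |
| 60% v 70% (assumed) | 0.95 | 1.07 | 1.11 | 1.19 |

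At m = 1 there is no bias. The endpoint is any response, so the Day 28 rates in the first row are only a stand-in; the documents give no any-response rates and no value of m.

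**The case against.** **Silence is not a choice.** A reader might infer that the protocol prescribes unstratified models, or that the missing Part 2 SAP is a planning fault. The documents support neither. Protocol 13.4.2 simply does not mention the stratum, and a Part 2 SAP could have added it and defined duration, as the Part 1 SAP did. There is no Part 2 SAP because the sponsor terminated the study with one subject enrolled (SAP sections 1 and 5.3). This explanation stands. What remains is that the protocol names the stratum for the binary endpoints and not for these, so the models as written contain treatment only.

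**The endpoints were never powered.** True, and this limits the weight of any power loss.

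**The larger figures fit one endpoint.** Also true. The 16-point gap at r = 4 is for overall survival to Day 365 and cannot be read across to failure-free survival or mortality, where it is about 9 points at Day 180.

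**A stratified fit is not the only remedy.** Entering the stratum as a covariate uses the same information and is equally acceptable.

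**The duration bias is conjecture.** Its size is. The responders-only reading is an inference for Part 2, and m is assumed. A reader might infer a bias against GLASSIA, but the direction depends on m and nothing in the documents fixes it. What stands is that the comparison would not be between randomised groups.

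**Conclusion.** The point holds, and it is minor. As written, the Part 2 Cox and competing-risk analyses leave out the factor used in randomisation. The cost is an HR pulled towards 1 (0.61 to 0.66 instead of 0.60 at Day 365 for stratum HR 2 to 4) and some loss of power: about 4 to 16 points for overall survival to Day 365, 2 to 9 at Day 180 and 1 to 5 at Day 100. These sizes rest on an assumed treatment HR, control survival and stratum HR, and one exponential survival curve stands in for every endpoint. If the stratum is not prognostic, the loss is nil. It would be too strong to say that type I error is at risk, or that only power is lost.

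For duration of response, the documents support saying that a two-arm Cox model is planned with no Part 2 population, start or end, and that a responders-only HR would not be a randomised comparison. They do not support a stated size or direction of bias.

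The primary and key secondary endpoints are unaffected. Part 2 never started, so no result is affected; the point matters if this plan is reused.

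**What to change.** - In protocol 13.4.2 and the synopsis, state that every Part 2 Cox and competing-risk model uses the randomisation stratum, either as a stratified fit or as a covariate. This is one sentence and a line of code, with no new data.
- For duration of any overall and any GI response, state the population, start, end and censoring rule for Part 2, and label responders-only curves and any HR from them descriptive.
- If a formal comparison of durability is wanted, use all randomised subjects with non-responders at zero, for example mean time in response up to a fixed day. The price is that this measure mixes how many respond with how long they respond, and it needs a stated censoring rule for subjects who stop treatment early.

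A separate matter bears on that rule. Protocol 8.2 (Treatment Failures) has all subjects followed at Days 100, 180 and 365, while 10.6 says that subjects who stop study treatment attend no visits beyond Day 28 and the termination visit, except to follow up adverse events. These passages must be reconciled.
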